#### 4.2 Schedule of Assessments

An overview of the schedule of assessments for the study is provided in Table 1.

Table 1 Schedule of Assessments – Overview of Study

Procedure/Assessment	Screening	Injection 1	Injection 2	Injection 3	Injection 4	Injection 5	ET / EOT 	Safety Follow up 
Visit Number	3	1	2	3	4	5	6	7
Day(s)		1	29	57	85	113	141	169
Window (days)		+2	-2 / +7	-2 / +7	-2 / +7	-2 / +7	-2 / +7	-7 / +7
Informed Consent 	X							
Inclusion/Exclusion Criteria	X			2				
Demographics 	403 							
Medical/Psychiatric History 	403 			3.				
Substance/Drug Use History 	403 							
Height 	403 							
Weight/BMI 	403 EOT 							
Urine Pregnancy Test 	403 EOT 		X	X	X	X	X	
UDS 	403 EOT 		X	X	X	X	X	
Injection Site Evaluation 	403 EOT 		X	X	X	X	X	
AE Assessment	X 		X	X	X	X	X	
Concomitant Medications	X 		X	X	X	X	X	X
Study Drug Administration		X	X	X	X	X		
MOUD and treatment History 	X							
Counselling 	2			X	ı	1		3.

AE=adverse event; BMI=body mass index; EOT=End-of-Treatment; ET=Early Termination; OUD=opioid use disorder; UDS=urine drug screen; MOUD=medication for opioid use disorder

Written informed consent must be obtained after completion of all INDV-6000-403 EOT procedures and before any INDV-6000-404 study-specific assessments/procedures are initiated.

2. This data will not be re-collected; the data from the INDV-6000-403 screening visit will be used.

- 3. This data will not be re-collected; the data from the INDV-6000-403 EOT visit will be used.
- 4. Any ongoing (at the INDV-6000-403 EOT) or new AEs or concomitant medications in this study will be recorded.
- 5. Required for female subjects of childbearing potential only, to be performed before SUBLOCADE dosing at Visits 1 to 6.
- 6. Qualitative test to be performed before SUBLOCADE dosing at Visits 1 to 6.
- 7. Injection site will be evaluated for signs of attempted removal before SUBLOCADE dosing at Visits 1 to 6. Any injection site reactions or infections will be recorded as AEs.
- 8. All subjects will receive counselling as determined by local standard of care throughout the study from Day 1 through EOT.
- 9. All subjects who receive SUBLOCADE (including those who wish to discontinue early), will be encouraged to attend the EOT visit 4 weeks after SUBLOCADE administration.
- 10. Any subject with ongoing AEs or concomitant medications at the EOT/ET Visit will also be followed up by telephone 4 weeks later for a safety follow up to assess the ongoing AEs or concomitant medications only.
- 11. A detailed detox and MOUD treatment history will be collected at screening. For those subjects who have enrolled in the study prior to approval of protocol amendment 1, their detox and MOUD treatment history will be collected retrospectively at their next visit.

#### 5 POPULATION

#### 5.1 Number of Subjects

Up to 25 adult subjects with moderate or severe OUD who are seeking MOUD and have completed the EOT Visit for the INDV-6000-403 study are planned to be enrolled into the study.

#### 5.2 Inclusion Criteria

Subjects must meet all the following criteria to be eligible for the study:

- 1. Signed the informed consent form (ICF) and have the ability to comply with the requirements and restrictions listed therein.
- 2. Completed the EOT Visit for the INDV-6000-403 Study.
- 3. Is an appropriate candidate in the opinion of the Investigator or medically qualified sub-Investigator.

#### 5.3 Exclusion Criteria

Subjects who meet any of the following criteria will be excluded from the study:

- 1. Subject compliance issues during participation in the INDV-6000-403 study which, in the opinion of the Investigator, could potentially compromise subject safety.
- 2. Subjects who are unable, in the opinion of the Investigator or Indivior, to comply fully with the study requirements including those who are currently incarcerated or pending incarceration/legal action.

#### 5.4 Subject Screening

Subjects who provide written informed consent will have their INDV-6000-403 assessments (per Table 1) re-reviewed to confirm study eligibility.

#### 5.5 Deviation from Inclusion/Exclusion Criteria

Waivers from inclusion and exclusion criteria are not allowed because they have the potential to jeopardise subject safety, the scientific integrity of the study or regulatory acceptability of the data. Indivior does not grant waivers to the protocol-defined inclusion and exclusion criteria, and strict adherence to these criteria as outlined in the protocol is essential.

# **6 STUDY CONDUCT**

# 6.1 Subject Screening

Study screening begins once written informed consent is obtained; the same subject identification number from INDV-6000-403 will be assigned. The subject identification number will be used to identify the subject during the screening process and throughout study participation, if applicable.

The Investigator is responsible for maintaining a master list (i.e., a subject identification list) of all consented subjects and will document all subjects that do not meet study eligibility criteria (i.e., screen failures), including reason(s) for ineligibility (i.e., a subject screening and enrolment log). This document will be reviewed by Indivior or designated representative for accuracy and completeness. Ineligible subjects, as defined by the protocol-specific inclusion and exclusion criteria, should not receive study drug and should be documented as screen failures.

#### 6.2 Enrolled

A subject will be considered enrolled if he/she receives at least 1 dose of SUBLOCADE.

#### 6.3 Not Enrolled

A subject will be considered not enrolled if written informed consent is obtained but the subject does not receive SUBLOCADE. Reasons for not enrolling (e.g., withdrawal of consent, does/not meet specified inclusion or exclusion criteria) will be recorded in the case report form (CRF).

#### 6.4 Treatment Period

Treatment period begins when the SUBLOCADE injection is given on Day 1 and ends after all assessments have been made at the EOT Visit.

# 6.5 Treatment Period Completion

A subject will be considered as completing the treatment period if they have received Injection 1 and Injection 5.

# 6.6 Study Completion

A subject will be considered to have completed the study if they have completed the last injection visit (Injection 5) and the scheduled EOT visit.

## 6.7 Early Termination

A subject will be considered an Early Termination if he/she is dosed with SUBLOCADE and does not complete the study (did not complete the last injection visit [Injection 5]) and the scheduled EOT visit.

Reasons for early termination (e.g., withdrawal of consent, lost to follow up, identification / move to alternative treatment site) will be recorded in the CRF. Subjects who Early Terminate from the study will be encouraged to attend the ET visit 4 weeks after SUBLOCADE administration, as well as a safety follow up via telephone if any AEs and concomitant medications are ongoing at the time of the ET visit.

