# 4 STUDY PLAN

# 4.1 Study Design

This is a single center, open-label, SUBLOCADE treatment extension study in which up to 25 subjects diagnosed with moderate or severe OUD will be enrolled. A subject is defined as enrolled when the first dose of SUBLOCADE is administered for this study.

Only subjects who have completed the End of Treatment (EOT) procedures for Study INDV-6000-403, have signed the INDV-6000-404 informed consent form (ICF), and meet all the enrollment criteria may be considered for inclusion in this study.

The INDV-6000-403 EOT visit is 28 days after the subjects first dose of SUBLOCADE in INDV-6000-403, therefore the INDV-6000-403 EOT and the INDV-6000-404 screening and Day 1 visit for this study will occur within 2 days.

The ICF may be shared with the potential subject before the INDV-6000-403 EOT Visit to discuss this study as a possible treatment option. However, the ICF must not be signed until all assessments for the INDV-6000-403 EOT Visit are complete.

The INDV-6000-403 EOT assessments will serve as the screening assessments for the Screening Visit (Day 1) of this study. Any AEs and concomitant medications ongoing at the INDV-6000-403 EOT will be re-recorded for this study. In addition, demographics, height, medical/psychiatric, substance and drug of abuse history will not be re-collected and will be taken from the INDV-6000-403 screening assessments. A detailed detox and MOUD treatment history will be collected at screening. For those subjects who have enrolled in the study prior to approval of protocol amendment 1, their detox and MOUD treatment history will be collected retrospectively at their next visit.

On Day 1, eligible subjects will receive a SC injection of 300mg SUBLOCADE. Before departing the site, any new adverse events (AEs) or concomitant medications will be recorded.

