Subjects will return to the site for monthly injection visits every 4 weeks (-2 / +7 days) for a total of up to 5 injections. At Injection Visits 2 through 5, subjects will be evaluated in accordance with local standard of care and results for the following procedures will be recorded: urine pregnancy test (to be performed before SUBLOCADE administration for all female subjects who are of childbearing potential); urine drug screen (UDS) and evaluation of previous injection site for potential reaction and evidence of attempts to remove the depot. For injections 2 to 5, subjects may receive either a dose of 100 mg SUBLOCADE or 300 mg SUBLOCADE, based on the medical judgment of the Investigator, per the SUBLOCADE USPI. During each visit the subject will be assessed for AEs and use of concomitant medications.

All subjects will receive counselling as determined by local standard of care throughout the study from Day 1 through EOT.

All subjects who receive SUBLOCADE (including those who wish to discontinue early), will be encouraged to attend the EOT/ET visit 4 weeks after SUBLOCADE administration.

At the EOT/ET Visit, results for the following procedures and assessments will be recorded: urine pregnancy test for all female subjects who are of childbearing potential; evaluation of previous injection site for potential reaction and evidence of attempts to remove the depot; UDS; use of concomitant medications and assessment for AEs. At every Visit options for continued care should be discussed with the subject.

Any subject with ongoing AEs or concomitant medications at the EOT Visit will also be followed up by telephone 4 weeks later for a safety follow up to assess the ongoing AEs or concomitant medications only.

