## 6.8.2 Subject Withdrawal of Consent

If a subject withdraws consent, the subject will not receive any additional doses of study drug. However, the subject may be offered additional tests as needed to monitor safety (e.g., EOT safety assessments or procedures).

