# 6.8.3 Subjects Lost to Follow-up

In cases of a missed visit, the Investigator or designee must attempt to contact the subject and re-schedule as soon as possible. The Investigator or designee must counsel the subject on the importance of maintaining the assigned visit schedule and ascertain whether or not the subject wishes to and/or should continue in the study.

In the event a subject is lost to follow-up, the Investigator or designee must make a reasonable effort to contact the subject. Two documented attempts (e.g., telephone, email, etc.) to contact the subject followed by a certified mailed letter is considered reasonable.

For the purpose of documenting date of discontinuation for a subject confirmed to be lost to follow-up, the date of discontinuation should be the date of last contact with the subject.

In the case where a certified letter is sent but not confirmed as received by the subject, the date of discontinuation is the date the certified letter was sent.

In the case where a certified letter is sent and has been confirmed as received by the subject, the date of discontinuation is the date of the confirmed subject receipt.

In the event that neither of these above cases applies (which should be explained in the source documents), the date of discontinuation is the date of the subject's last study visit.

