## **10.2** Assessing and Documenting Adverse Events

The Investigator is ultimately responsible for assessing and reporting all AEs as outlined in the protocol. The assessment and reporting of AEs may be delegated to a medically qualified sub-Investigator, trained on this study protocol, who is listed on the delegation of authority log. All AEs regardless of suspected causal relationship to the study drug will be reported as described in this protocol.

Adverse events should be volunteered by the subject or solicited from the subject using a standard statement, obtained from examination of the subject at a clinic visit, or from observations of clinically significant laboratory values or special examination abnormal values.

All AEs are to be assessed and recorded in a timely manner and followed to resolution or until the Investigator determines that there is not an anticipated resolution. Each AE is to be documented with reference to severity, date of occurrence, duration, treatment and outcome. Furthermore, each AE is to be classified as being serious or non-serious. In addition, the Investigator must assess whether the AE is study drug-related or not.

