4 POPULATIONS FOR ANALYSIS

The safety population will consist of all subjects who received at least 1 dose of SUBLOCADE in this study and will be the primary population for all analyses. All subjects who were screened received SUBLOCADE. Therefore, a screened population was not defined as it would comprise the same set of subjects.

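### A dosed subject who misses the EOT/ET visit and is not rescheduled has no required adverse event enquiry after the last injection visit, yet stays in the denominator of the primary proportion

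*Protocol*

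**What the plan says.** **Scheduled assessments.** Protocol Table 1 (repeated as SAP Table 3) marks an AE assessment at screening, at Injections 2 to 5 and at ET/EOT. On Day 1, Protocol 4.1 adds: "Before departing the site, any new adverse events (AEs) or concomitant medications will be recorded".

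**Attendance.** Under Protocol 4.1, all dosed subjects, including those stopping early, "will be encouraged to attend the EOT/ET visit 4 weeks after SUBLOCADE administration". Section 6.7 repeats the encouragement for early terminators.

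**The later call.** Footnote 10 of Table 1 states: "Any subject with ongoing AEs or concomitant medications at the EOT/ET Visit will also be followed up by telephone 4 weeks later". Section 6.7 words it for early terminators as "as well as a safety follow up via telephone if any AEs and concomitant medications are ongoing at the time of the ET visit". Sections 4.1 and 10.3 also tie the call to matters ongoing at EOT. Section 10.3 collects AEs up to completion of the EOT visit.

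**Missed visits and withdrawal.** After a missed visit, Section 6.8.3 says that the investigator or designee "must attempt to contact the subject and re-schedule as soon as possible", counsel the subject on keeping to the schedule and establish whether the subject will continue. For loss to follow-up it treats two documented attempts and a certified letter as reasonable. It mentions no AE question. After withdrawal of consent, Section 6.8.2 says that "the subject may be offered additional tests as needed to monitor safety".

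**Counting.** SAP 4 defines the Safety population as "all subjects who received at least 1 dose of SUBLOCADE in this study and will be the primary population for all analyses". SAP 5.3.2 gives the number and percentage of subjects reporting TEAEs. SAP 5.1.5 and 6.5 use observed data, and the only AE rule in SAP 6.5 concerns incomplete or missing start dates.

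**The concern.** The last scheduled AE question and the trigger for the later call both sit in one visit. If that visit does not take place, both are lost. The site must still try to reach the subject, but it is not told to ask about AEs when it succeeds.

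Non-attendance is foreseeable. The study supports subjects while they look for longer-term care, and Section 6.7 itself lists loss to follow-up and a move to another treatment site as reasons for early termination.

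An unasked interval then looks the same in the primary result as an interval in which the subject was asked and reported nothing. The error runs one way, because a TEAE that is not elicited can only lower the proportion. It matters most when few AEs are recorded, since a reader needs to know whether none means asked and none.

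**Working it through.** **1. Is there another required AE enquiry for a non-attender?**

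- *Missed-visit contact (Protocol 6.8.3):* required, but for rescheduling, counselling and continuation. If the visit is rescheduled and kept, the AE question is restored. If not, none is required.
- *4-week call (4.1, footnote 10, 6.7, 10.3):* depends on findings at EOT/ET, so it cannot be triggered without that visit.
- *Consent withdrawal (6.8.2):* further safety tests are optional.
- *General AE rule (10.2):* "Adverse events should be volunteered by the subject or solicited from the subject using a standard statement". This says how AEs are obtained and schedules no contact.
- *SAE reporting (11.2.1):* starts when the site becomes aware of the event.

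None of these requires anyone to ask.

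**2. How is such a subject counted?** The denominator is every dosed subject (SAP 4), the numerator is subjects reporting a TEAE (SAP 5.3.2), data are used as observed (SAP 5.1.5, 6.5), and no rule covers absent AE ascertainment. The subject is therefore in the denominator, and in the numerator only if an event was recorded anyway.

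**3. Share of time not asked about.** Table 1 places injections on Days 1, 29, 57, 85 and 113 and EOT on Day 141. After k injections, nominal time to ET is 28k days, of which the last 28 are not asked about: 28/(28k) = 1/k.

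| Injections received (k) | 1 | 2 | 3 | 4 | 5 |
|---|---|---|---|---|---|
| Share not asked about | 100% (apart from the Day 1 record) | 50% | 33% | 25% | 20% |

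**4. Ceiling per subject.** A subject with no earlier TEAE can move the proportion by at most 1/N: 1/25 = 4.0 points, 1/20 = 5.0 points, 1/15 = 6.7 points. The plan gives only a maximum of 25; the smaller N are illustrative.

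With x subjects with a recorded TEAE and m affected subjects without one, the possible range is x/N to (x+m)/N. At N=25 and m=5 this is 0% to 20% if x=0, and 3/25 to 8/25 = 12% to 32% if x=3.

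**5. Expected size.** The documents state no power, precision, dropout or TEAE rate, so there is no planned figure to reproduce and all rates here are assumptions. Take a constant hazard and a 140-day TEAE proportion p. The 28-day risk is q = 1 − (1−p)^(1/5), which gives 0.0209, 0.0689 and 0.1674 for p = 0.1, 0.3 and 0.6. The expected undercount for one non-attender after k injections is (1−p)^((k−1)/5) × q. For five non-attenders, in subjects:

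| k | p = 0.1 | p = 0.3 | p = 0.6 |
|---|---|---|---|
| 1 | 0.10 | 0.34 | 0.84 |
| 3 | 0.10 | 0.30 | 0.58 |
| 5 | 0.10 | 0.26 | 0.40 |

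Divided by 25, this is about 0.4 to 3.3 points. One non-attender gives 0.02 to 0.17 subjects, or 0.1 to 0.7 points.

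A wider assumption sets q directly at 10% to 30%, with 2 to 10 affected subjects who have no earlier TEAE. The result runs from 2 × 0.1/25 = 0.8 points to 10 × 0.3/25 = 12.0 points. The upper end needs 10 of 25 subjects affected and a 28-day risk that implies a 140-day proportion of 1 − 0.7^5 = 83%.

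**The case against.** The best defence is that the plan does schedule the question: Table 1 marks it at ET/EOT, and Section 6.8.3 requires an attempt to rebook a missed visit. That stands, and a reader who inferred that no AE question is scheduled after the last injection would be wrong. The remaining gap is the subject who is reached but does not come. For those who cannot be reached, an extra question achieves nothing. For those who withdraw consent, optional wording is to be expected.

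A reader might also infer that the planned outputs hide non-attendance. They do not. Study completion requires the EOT visit (SAP 5.1.4.5), so an Injection 5 recipient who skips it is already counted as discontinued. Doses received are tabulated (SAP 5.5.2), urine drug screens are summarised by visit (SAP 5.5.7), and by-subject listings are planned (SAP 5.1.5). With at most 25 subjects, attendance can largely be reconstructed. What is missing is one stated count placed beside the TEAE result.

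SAP 5.3.2, read alone, suggests that 6 or fewer AEs leave only a listing. SAP 5.1.5 and 5.5.1 keep the AE-occurrences table when at least one AE is reported. With 6 or fewer AEs no TEAE percentage is tabulated, so the counting problem then applies to how the listing is read.

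The treatment period ends at the EOT visit (Protocol 6.4, SAP 5.1.4.4), so it has no stated end for a non-attender. One might infer that reported events are lost for that reason. SAP 5.3.1 defines a TEAE by onset on or after first dose, so this excludes no reported event, and no new cutoff is needed.

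Finally, the study is descriptive, and sampling uncertainty is already wide: the exact 95% interval for 0/25 reaches 13.7%. That limits the importance of the gap but does not remove its one-sided direction.

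**Conclusion.** The point holds as a gap in ascertainment. A dosed subject who misses EOT/ET and is not rescheduled has no required AE enquiry after the last injection visit, and remains in the primary denominator. That such a subject counts as having no TEAE in that interval is an inference from the counting rules; neither document states it.

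The direction is certain: the proportion can only be understated. The size is at most 4.0 points per affected subject at N=25, and only for subjects with no earlier TEAE. In expectation it is probably much smaller: about 0.4 to 3.3 points for five non-attenders under constant hazard and an assumed 140-day proportion of 10% to 60%. More extreme assumptions reach 12 points. None of these rates comes from the documents. Subjects who attend EOT/ET are unaffected.

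This is a cheap improvement to safety collection and reporting, and does not invalidate the primary analysis.

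**What to change.** **If follow-up is still open,** amend Protocol 6.7 and 6.8.3 for any dosed subject who misses EOT/ET and has not withdrawn consent to contact:

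- ask about new and ongoing AEs and SAEs at the contact attempts already required;
- make the existing 4-week call whether or not an ET visit took place.

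**In either case,** add one row to the SAP 5.2 disposition table giving the number of dosed subjects with no AE assessment after their last injection. Cite it beside the TEAE result, or beside the AE listing if there are 6 or fewer AEs. Giving the range x/N to (x+m)/N as well is optional.

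**Cost.** The reporting part is one table row and needs no new data. The collection part is a minor amendment and a short call for a few subjects. It may add a few AEs, some arising under other treatment. Subjects who cannot be reached stay unassessed, which is why the count should be reported.

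**Timing.** SAP version 2.0 (02 Jul 2020) describes screening and dosing in the past tense. Its version history also says that no AEs were reported, which may refer only to AEs of special interest. The amendment may therefore be too late, in which case the reporting part is the usable one.

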# 6.8 Withdrawal and Stopping Criteria

# 6.8.1 Subject Withdrawal from the Study

If the subject has discontinued study treatment (including depot removal) and is no longer being followed for study assessments and procedures (including follow-up procedures), he/she will be considered withdrawn from the study. The primary reason for withdrawing from the study must be entered into the CRF (e.g., subject is lost to follow-up, Indivior terminates the study or Investigator's discretion).

